## 5. STATISTICAL ANALYSES

### 5.1. General Considerations

The SAP will use throughout the document the following definitions:

- Study treatment refers to: JNJ-3989, NA, and PegIFN- $\alpha$ 2a
- Study agent refers to: JNJ-3989, NA, and PegIFN- $\alpha$ 2a
- Study intervention arm refers to:
  - Arm 1: JNJ-3989 for 24 weeks + NA for 24 weeks + PegIFN- $\alpha$ 2a for 24 weeks.
  - Arm 2: JNJ-3989 for 24 weeks + NA for 24 weeks + PegIFN- $\alpha$ 2a from Week 12 till Week 24.
  - Arm 3: JNJ-3989 for 24 weeks + NA for 24 weeks + PegIFN- $\alpha$ 2a from baseline till Week 12.

### 5.1.1. Analysis Phase

The analyses phases are defined in [Table 3](#) below.

**Table 3: Analysis Phases Start and End Dates**

Analysis Phase	Start Date	End Date
Screening	The date of signing the informed consent	1 day before the first study agent intake
Treatment period	Date of first study agent intake	
If participant did not withdraw from the study and did not discontinue treatment early prior to the projected/actual Week 24 Visit date:
 
Min [Date of Week 24 study agent intake – 1 day, cut-off dateb]
 
Otherwise:
 
Max [Early study withdrawal visit date, study agent discontinuation date] + 5 daysa or cut-off dateb, whichever occurs first

Follow-up	
Participants who did not withdraw informed consent during treatment period: End of treatment period + 1 day
 
Otherwise: missing
	Max [study discontinuation date, study completion date] or cut-off date b , whichever occurs first

a Addition of 5 days is only applicable for Adverse Events and Concomitant Medications.

b Cut-off dates will be defined to match the prespecified timepoints for DRC safety monitoring, interim analyses, the primary and the final analyses, respectively.

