AFP: alpha fetoprotein; ALP: alkaline phosphatase; ALT: alanine aminotransferase; AST: aspartate aminotransferase; CKD EPI: Chronic Kidney Disease Epidemiology Collaboration; CRF: case report form; CT: computed tomography; D/d: day; DAIDS: Division of Acquired Immunodeficiency Syndrome; DBP: diastolic blood pressure; DNA: deoxyribonucleic acid; ECG: electrocardiogram; eGFR: estimated glomerular filtration rate; EOS: end of study; EOSI: end of study intervention; FSH: follicle stimulating hormone; FU: follow up; GI: giga; HBeAg: hepatitis B core protein; HBe(Ag): hepatitis B e (antigen); HBcrAg: hepatitis B core related antigen; HBs(Ag): hepatitis B surface (antigen); HBV: hepatitis B virus; HCC: hepatocellular carcinoma; HIV 1 (2): human immunodeficiency virus type 1 (type 2); HLA: human leukocyte antigen; ICF: informed consent form; IgM: immunoglobulin M; INR: International Normalized Ratio; ISA: intervention specific appendix; MRI: magnetic resonance imaging; NA: nucleos(t)ide analog; PBMC: peripheral blood mononuclear cells; PegIFN α2a: pegylated interferon alpha 2a; PK: pharmacokinetic; RBC: red blood cell; RNA: ribonucleic acid; SBP: systolic blood pressure; T4: thyroxine; TSH: thyroid stimulating hormone; ULN: upper limit of normal; W: week; WD: withdrawal.

- a. All study visits are to be scheduled relative to the baseline (Day 1) visit date. All follow up study visits are to be scheduled relative to the Week 24/EOSI/WD visit. An unscheduled visit can be performed upon the investigator’s discretion, in case of HBV DNA elevations, ALT elevations, other signs of worsening of liver disease, or for any other reason.
- b. At all visits, blood samples should be collected before administration/intake of study intervention (JNJ 3989, PegIFN α2a, and NA), unless indicated otherwise.
- c. Participants who discontinue study intervention early will have an early WD visit and will enter follow up unless they withdraw consent. Participants who withdraw consent will be offered an optional safety follow up visit to occur on the day of consent withdrawal. For the optional safety follow up visit, assessments are at the investigator’s discretion and could be similar to the early WD visit.

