All participants will receive the last dose of JNJ-3989 at Week 24 and the last dose of PegIFN- α 2a at Week 23 (Arms 1 and 2) or Week 11 (Arm 3). They will start the FU Period after the Week 24 visit. If the protocol-defined NA treatment completion criteria (see Section 6.5.1, NA Treatment Completion, for more details) are met based on the Week 24 results, NA will be stopped at the next scheduled visit (ie, FU Week 2), otherwise NA treatment will continue during the complete FU Period. **Note:** Participants who are close to meeting the protocol-defined NA treatment completion criteria with the Week 24 results, and do meet the criteria based on the FU Week 2 results may be allowed to stop NA at FU Week 4, after consultation with the Sponsor.

Participants who meet the protocol-defined NA treatment completion criteria will be monitored closely during the 48-week FU Period with a study visit at least once every 4 weeks. NA treatment should be re-started in accordance with the NA re-treatment criteria (see Section 6.5.2, NA Re-treatment Criteria During Follow-up, for more details).

Study intervention consists of:

- JNJ-3989: 200 mg subcutaneous injection Q4W
- NA: tenofovir disoproxil (245 mg), or TAF (25 mg), or ETV (0.5 mg) tablets p.o. QD
- PegIFN- α 2a: 180 μ g subcutaneous injection QW.

Both the Platform Master informed consent form (ICF) and the ISA ICF must be signed before the first study-related activity takes place.

Assessments and sampling include:

- Safety and tolerability, based on AEs, laboratory assessments, ECGs, vital signs, ophthalmologic and physical examination, will be assessed throughout the study from the time that the ISA ICF is signed until the completion of the last study-related activity (see Section 8.2, Safety Assessments, and Section 8.3, Adverse Events and Serious Adverse Events).
- Efficacy will be evaluated using different parameters including HBsAg, HBeAg, and HBV DNA (see Section 8.1, Efficacy Assessments).
- Samples for HBV genome sequencing will be taken at the time points indicated in the [Schedule of Activities](#) (see Section 8.1.1, Sequencing). Samples may be sequenced based on the Sponsor virologist's request, considering the HBV DNA levels. In case of a virologic breakthrough/flare, additional samples for viral sequencing may be taken.

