## 5.1.3. Visit Windows

As participants do not always adhere to the protocol visit schedule, the following rules are applied to assign actual visits to analysis visits. All visits for all assessments (safety, efficacy or PK) will be uniquely allocated within each phase to an analysis time point based on the analysis relative day (ADY) compared with the target day based on [Table 4](#). All assignments will be made in chronological order. Once a visit date is assigned to a visit window, it will no longer be used for a later time point except for the end of treatment period and end of study (EOS) visits. If a participant has 2 or more actual visits in 1 visit window, the visit closest to the target day will be used as the protocol visit for that visit window. The other additional visit(s) will not be used in the summaries or analyses, but they can be used for determination of clinically important endpoints. If 2 actual visits are equidistant from the target day within a visit window, the later visit is used. If there are two or more measurements on the same day, then the last measurement in chronological order will be used. If the time of the assessment is not available, the highest record/sequence number will be selected.

The listings will include all measurements, also those multiple assessments with the same visit window/phase.

End of treatment (EOT) and end of study (EOS) time points will be included in all analyses over time unless otherwise stated.

Table 4 provides the analysis time points and time intervals for each visit per analysis phase.

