**Table 4: Visit Windows**

Analysis phase	Target Day	Analysis time point (Week)	Analysis time point (label)	Time interval (days)
Screening	$-\infty$	-1	Screening	<0
Treatment period	1	0	Baseline	Pre-dose: 1
	15	2	Week 2	[2, 22]
	29	4	Week 4	[23, 43]
	57	8	Week 8	[44, 71]
	85	12	Week 12	[72, 92]
	99	14	Week 14	[93, 106]
	113	16	Week 16	[107, 127]
	141	20	Week 20	[128, 155]
	169	24	Week 24	[156, 183]
		Last visit in treatment period	25 a	EOT a
Follow-up	15	26	Follow-up Week 2	[1, 22]
	29	28	Follow-up Week 4	[23, 43]
	57	32	Follow-up Week 8	[44, 71]
	85	36	Follow-up Week 12	[72, 99]
	113	40	Follow-up Week 16	[100, 127]
	141	44	Follow-up Week 20	[128, 155]
	169	48	Follow-up Week 24	[156, 183]
	197	52	Follow-up Week 28	[184, 211]
	225	56	Follow-up Week 32	[212, 239]
	253	60	Follow-up Week 36	[240, 267]
	281	64	Follow-up Week 40	[268, 295]
	309	68	Follow-up Week 44	[296, 323]
	337	72	Follow-up Week 48	[324, $+\infty$ ]
	Last visit in the study	999 b	EOS b	

a End of treatment (EOT) visit will be the last post-baseline visit in treatment period.

b End of study (EOS) visit (last available data during the follow-up visit) will be the last visit in the study.

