### **5.3.2.1.4. Missing Data Handling Rule**

Participants who withdraw from the study prior to Week 24 will be considered as non-responders.

If a participant remains in the study after experiencing a major protocol deviation (defined for the purpose of efficacy analyses and is an intercurrent event) and has missing Week 24 value, then the imputation to non-response will be applied. If the value for the endpoint at Week 24 is available, then such data will be used to determine their response status.

For the participants still in the study at Week 24 or for participants that have neither discontinued treatment early nor experienced any major protocol violations (defined for the purpose of efficacy analyses and is an intercurrent event), and HBsAg values missing at Week 24, then the primary method to handle missing data will be the missing as non-responder (MANR).

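### SAP Tables 3 and 4 contradict each other on which phase holds the Week 24 visit; read literally, Table 3 leaves the primary endpoint's time point empty for completers

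*SAP*

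**What the plan says.** **Phase boundaries (SAP 5.1.1, Table 3).** For a participant who neither withdraws nor stops treatment early, the treatment period ends at "Date of Week 24 study agent intake – 1 day", or at the data cut-off if that is earlier. Follow-up begins at "End of treatment period + 1 day". Early discontinuers have a different rule, "Max [Early study withdrawal visit date, study agent discontinuation date] + 5 days" (the 5 days apply to adverse events and concomitant medications only), so their last visit stays in the treatment period.

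**Allocation (SAP 5.1.2.2 and 5.1.3).** FU Day 1 is the follow-up start date from Table 3. Visits "will be uniquely allocated within each phase to an analysis time point based on the analysis relative day (ADY"). Phase is therefore settled first, and the window is applied inside the phase.

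**Windows (SAP Table 4).** Week 24 is listed under the treatment period, target day 169, days 156 to 183. Week 20 has target day 141, days 128 to 155. FU Week 2 has target FU day 15, FU days 1 to 22. Only Baseline carries a pre-dose qualifier. "End of treatment (EOT) visit will be the last post-baseline visit in treatment period".

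**Dosing and sampling (Protocol 4.1 and 1.3).** "All participants will receive the last dose of JNJ-3989 at Week 24". The Schedule of Activities (footnote b) requires that at all visits "blood samples should be collected before administration/intake of study intervention", and footnote n has NA taken on site at visits. The Week 24 sample and the Week 24 intake therefore share a date.

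**Missing Week 24 value (SAP 5.3.2.1.4).** For participants still in the study with no Week 24 HBsAg, "the primary method to handle missing data will be the missing as non-responder (MANR").

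**The concern.** Table 3 works in calendar dates. A sample drawn before the dose on the Week 24 date is on that date all the same, so Table 3 sends it to follow-up. Table 4 expects to find it in the treatment period. Nothing in the SAP says which table governs.

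The primary endpoint is read at this time point. Other outputs depend on the same boundary:

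- NA treatment completion at Week 24 (SAP 5.4.1.1.1, 5.4.2.1.2) and treatment failure (5.4.1.1.6) use the same visit.
- EOT, defined as the last post-baseline visit in the treatment period, would become the Week 20 visit.
- The NA reference timepoint (SAP 5.1.6) is the last value before follow-up starts, so it would also become the Week 20 value.

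The last two are harder to spot than an empty primary table, because they would be filled with plausible but wrong data. The study is open-label, and the study team sees interim results that include a Week 24 look on about half the participants before the primary analysis (Protocol 9.5, SAP 5.8.3.2). An undocumented choice about the primary derivation is best avoided in that setting.

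**Working it through.** **Inputs.** Phase rules from SAP Table 3; day formula from SAP 5.1.2; windows from SAP Table 4; visit tolerances from the Schedule of Activities (Week 20 and Week 24 ±3 days, FU Week 2 ±4 days). The sample and the dose are taken to fall on the same date.

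**1. The plan's own target days.** 24 × 7 + 1 = 169 and 20 × 7 + 1 = 141. Both match Table 4.

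**2. Phase boundary, nominal schedule.** Treatment period ends on day 169 − 1 = 168. Follow-up starts on day 168 + 1 = 169, the Week 24 date.

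**3. Where the Week 24 sample goes.** FU day = visit date − FU start + 1 = 169 − 169 + 1 = 1. That lies in [1, 22], the FU Week 2 window.

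**4. Whether another scheduled visit can fill Week 24.** The latest in-window Week 20 visit is day 141 + 3 = 144. The Week 24 window opens on day 156. It cannot.

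**5. What happens inside the FU Week 2 window.** The FU Week 2 visit, 14 days after Week 24, is FU day 15, at distance 0 from target. With the ±4-day tolerance it lies on FU days 11 to 19, at most 4 days from target. The Week 24 sample on FU day 1 is 14 days from target. The closest-to-target rule keeps the FU Week 2 visit, and the Week 24 sample drops out of the by-visit analysis.

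**6. All in-window schedules.** Week 20 on days 138 to 144 (7 values), Week 24 on days 166 to 172 (7 values), FU Week 2 at 10 to 18 days after Week 24 (9 values): 7 × 7 × 9 = 441.

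| Rule | Week 24 window empty | Week 24 sample chosen as FU Week 2 |
|---|---|---|
| Table 3 as written | 441 of 441 | 0 of 441 |
| Week 24 date kept in the treatment period | 0 of 441 | 0 of 441 |

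**7. What it would do to the primary test.** With 30 per arm, an exact test against 2% needs at least 3 responders at one-sided 0.05, and at least 4 at 0.05/3, the strictest Hochberg step. At a true rate of 32% (2% plus the planned 30-point difference), power is 99.9% and 99.5% at these two levels, consistent with the stated figure of more than 95%. The documents give no share of responders lost to the boundary rule, so the range below is an assumption.

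| Assumed share of responders recorded as missing | Power at 0.05 | Power at 0.05/3 |
|---|---|---|
| 25% | 98.6% | 95.2% |
| 50% | 88.0% | 73.0% |
| 75% | 43.5% | 21.6% |
| 100% (literal reading) | 0% | 0% |

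**The case against.** The best reply is that the intention is plain. Table 4 lists Week 24 under treatment, and SAP 5.3.1 defines the endpoint at Week 24 as the end of study intervention. A programmer who worked by nominal visit would keep the sample, and an empty primary time point in every arm would be seen at the first run. This stands, and it is why the point is a contradiction between two tables and not a rule that discards the data. It does not settle which table applies.

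Three passages might be offered as a rescue.

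- SAP 5.1.3 lets a visit be reused for the end-of-treatment time point. That does not help: under Table 3 the last treatment-period visit is Week 20.
- SAP 5.1.3 also lets extra visits in a window inform clinically important endpoints. That is permissive and does not name the primary endpoint.
- Sensitivity estimator 3 (SAP 5.3.2.2.3) takes the closest value within 4 weeks of Week 24 and could recover the sample. It is not the main estimator. Estimator 2 would drop these participants.

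The minus-1-day rule also has a use: it makes the FU Week 2 visit FU day 15, as Table 4 expects. The repair should preserve that.

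A reader might infer more than the documents support:

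- **All reference timepoints are wrong.** Only the NA one is defined by the start of follow-up. The PegIFN one precedes the first PegIFN dose in Arm 2, and the JNJ-3989 one is tied to stopping that drug.
- **Adverse events after the last JNJ-3989 dose are lost.** Every event at or after first administration stays treatment-emergent (SAP 5.6.2). Only the phase label changes, and the protocol itself starts follow-up at Week 24.
- **FU Week 2 results are widely contaminated.** That visit is not among the optional ones (Schedule of Activities, footnote d), and mislabelling arises only if it is missed.
- **The loss should be measured against response rates of 50% to 80%.** Those rates belong to the secondary pairwise comparisons (SAP 3), not to the test against 2%.

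**Conclusion.** The contradiction is real and affects the derivation of the primary endpoint, so it should be corrected before any Week 24 result is tabulated. Followed literally, Table 3 leaves Week 24 HBsAg missing for completers who attend on schedule, and the missing-data rule makes them non-responders. That would put every arm near 0%, below the 3 responders of 30 needed at the 0.05 level.

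That figure is the extreme of one reading. A reader might take it as the expected result of the trial; the documents do not support that, because Table 4 contradicts the rule that produces it.

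The result assumes that blood and dose share the Week 24 date, that phase is assigned before window, and that there is no unscheduled HBsAg sample between day 156 and the day before the Week 24 dose. A participant whose blood was drawn on an earlier date than the dose, or who had such an extra sample, could have a Week 24 value even under the literal rule. The sample-size figures are not in question.

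**What to change.** Add one explicit rule to SAP Tables 3 and 4: for completers, all assessments taken pre-dose on the Week 24 visit date belong to the treatment period and are eligible for Week 24 and EOT, in the way the pre-dose qualifier already works for Baseline.

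Then make the related text agree:

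- Keep the Week 24 date as FU Day 1 for calculating FU target days. Simply moving the end of treatment to the Week 24 date would shift the clock by a day and put the nominal FU Week 2 visit on FU day 14 against a target of 15.
- Change the FU Week 2 window from [1, 22] to [2, 22].
- Reword SAP 5.1.2.2, which takes FU Day 1 from Table 3, so that the FU day count and the phase allocation are stated separately.
- Reword the NA reference timepoint in SAP 5.1.6 so that the Week 24 pre-dose value qualifies.
- Give the Week 24 PK sample its own line. It is drawn 2 to 6 hours after dosing (Schedule of Activities, footnote qq), so it is neither pre-dose nor on FU day 2 or later.

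The cost is SAP wording and programming specifications. No new data, visits or samples are needed.

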## 5.1.2. Relative Day by Study Phase

An analysis relative day (ADY) will be calculated for all assessments at all visits for each participant by study phase.

### 5.1.2.1. Treatment Period Relative Day

Treatment period (TP) start date (TP Day 1) is defined in [Table 3](#). All efficacy and safety assessments during the treatment period will be assigned an analysis day relative to this date.

The study day in the treatment period phase (TP ADY) is defined as:

$$TP\ ADY = visit\ date - TP\ start\ date + 1$$

for visits on or after treatment period Day 1, and

$$TP\ ADY = visit\ date - TP\ start\ date$$

for visits before TP Day 0 (Screening phase).

There is no 'TP Day 0'.

### 5.1.2.2. Follow Up Relative Day

Follow-up (FU) start date (FU Day 1) is defined in [Table 3](#). Efficacy and safety assessments during the FU phase will be assigned a day relative to this date. The FU study day in the FU phase (ADY) is defined as:

$$FU\ ADY = visit\ date - FU\ start\ date + 1$$

for visits on or after FU Day 1.

## 5.1.3. Visit Windows

As participants do not always adhere to the protocol visit schedule, the following rules are applied to assign actual visits to analysis visits. All visits for all assessments (safety, efficacy or PK) will be uniquely allocated within each phase to an analysis time point based on the analysis relative day (ADY) compared with the target day based on [Table 4](#). All assignments will be made in chronological order. Once a visit date is assigned to a visit window, it will no longer be used for a later time point except for the end of treatment period and end of study (EOS) visits. If a participant has 2 or more actual visits in 1 visit window, the visit closest to the target day will be used as the protocol visit for that visit window. The other additional visit(s) will not be used in the summaries or analyses, but they can be used for determination of clinically important endpoints. If 2 actual visits are equidistant from the target day within a visit window, the later visit is used. If there are two or more measurements on the same day, then the last measurement in chronological order will be used. If the time of the assessment is not available, the highest record/sequence number will be selected.

The listings will include all measurements, also those multiple assessments with the same visit window/phase.

End of treatment (EOT) and end of study (EOS) time points will be included in all analyses over time unless otherwise stated.

Table 4 provides the analysis time points and time intervals for each visit per analysis phase.

**Table 4: Visit Windows**

Analysis phase	Target Day	Analysis time point (Week)	Analysis time point (label)	Time interval (days)
Screening	$-\infty$	-1	Screening	<0
Treatment period	1	0	Baseline	Pre-dose: 1
	15	2	Week 2	[2, 22]
	29	4	Week 4	[23, 43]
	57	8	Week 8	[44, 71]
	85	12	Week 12	[72, 92]
	99	14	Week 14	[93, 106]
	113	16	Week 16	[107, 127]
	141	20	Week 20	[128, 155]
	169	24	Week 24	[156, 183]
		Last visit in treatment period	25 a	EOT a
Follow-up	15	26	Follow-up Week 2	[1, 22]
	29	28	Follow-up Week 4	[23, 43]
	57	32	Follow-up Week 8	[44, 71]
	85	36	Follow-up Week 12	[72, 99]
	113	40	Follow-up Week 16	[100, 127]
	141	44	Follow-up Week 20	[128, 155]
	169	48	Follow-up Week 24	[156, 183]
	197	52	Follow-up Week 28	[184, 211]
	225	56	Follow-up Week 32	[212, 239]
	253	60	Follow-up Week 36	[240, 267]
	281	64	Follow-up Week 40	[268, 295]
	309	68	Follow-up Week 44	[296, 323]
	337	72	Follow-up Week 48	[324, $+\infty$ ]
	Last visit in the study	999 b	EOS b	

a End of treatment (EOT) visit will be the last post-baseline visit in treatment period.

b End of study (EOS) visit (last available data during the follow-up visit) will be the last visit in the study.

#### 5.1.4. Baseline

In general, the baseline assessment is defined as the last observed non-missing measurement before the date and time of the first administration of any of study agents.

In case the first administration measurement time is missing, the first observed measurement on TP Day 1 will be used as the baseline measurement. If no observed measurement on Day 1, the last observed measurement before Day 1 will be used as the baseline assessment.

### **5.1.5. Analysis Specifications**

In general, continuous variables will be summarized using descriptive statistics including the number of participants, mean, standard error (SE), standard deviation (SD), two-sided 90% confidence interval (CI), median, and range. The 90% CI for continuous endpoints is constructed using the t-distribution. Binary or categorical variables will be summarized using the number and percentage of participants in each category and 90% CI using Clopper-Pearson exact method for the simple sample proportion (Newcombe RG,1998). For time-to-event variables, using the Kaplan-Meier approach, a summary table including number of participants included in the analysis, number of participants censored, 25th and 75th percentiles, median time-to-event and 90% CI will be shown. Graphic displays will also be used to summarize the data.

